Accuracy of Ultra-Low-Dose CT (ULDCT) of the Chest Compared to Plain Film in an Unfiltered Emergency Patient Cohort

Study protocol and statistical analysis plan

English Version

Version 1.3
24th of April 2019

Table of contents

1	AUTHORS	3
2	PARTICIPANTS	3
3	PROJECT TITLE	4
4	BACKGROUND AND SUMMARY	5
5	STUDY DESIGN.....	7
6	HYPOTHESES AND OUTCOME MEASURES	10
7	INCLUSION CRITERIA	11
8	EXCLUSION CRITERIA	12
9	ETHICAL CONSIDERATIONS	12
10	RECRUITMENT	13
11	STUDY DURATION	13
12	RADIATION DOSE.....	13
13	RADIOLOGICAL ANALYSIS	14
14	STATISTICAL ANALYSIS PLAN	15
15	COMPENSATION	15
16	STUDY SUSPENSION	16
17	DATA MANAGEMENT AND DATA PROTECTION	16
18	FUNDING.....	16

ULDCT project

1 Authors

- Univ.[name].-Doz. Dr.med.univ. [name], MBA
- Mag.rer.soc.oec. Dr.med.univ. [name]
- Mag. [name]
- ao.Univ.-[name].-Ing. [name]
- Ass.-[name].-Doz. Dr.med.univ. [name], MBA
- Assoc.[name].-Doz. Dr.med.univ. [name]
- Dr.med.univ. [name]
- Assoc.[name].-Doz. Dr.med.univ. [name]
- Assoc.[name].-Doz. Dr.med.univ. [name]
- Assoc.[name].-Doz. Dr.med.univ. [name]
- Dr.med.univ. [name]
- o.Univ.-[name].med.univ. [name]
- ao.Univ.-[name].med.univ. [name]
- Ass.-[name].med.univ. [name]
- Dr.med.univ. [name]
- Dr.med.univ. [name]

2 Participants

Intended number of participants	250
Limiting age, minimum	18 years
Limiting age, maximum	92 years
Ability to provide informed consent	Yes
Male participants	Yes

Female participants	Yes
Duration of participation in the trial for each participant	Approximately two hours for each patient from inclusion in the study until the therapeutic consequences are established.
Active phase	Six months
Follow-ups	Within the trial no follow-up is intended. However, if clinically indicated follow-ups are performed, this data may be used in the analysis phase of the study for final diagnosis.
Estimated duration of the trial	One year (six months of acquisition, six months of evaluation)

3 Project title

Brief title

Accuracy of Ultra-Low-Dose-CT of the Chest Compared to Plain Film in an Unfiltered Emergency Department Patient Cohort

Acronym

UP-Chest

Official title

Accuracy of Ultra-low-dose-CT (ULDCT) of the Chest Compared to Plain Film in an Unfiltered Emergency Department Patient Cohort

4 Background and summary

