Initial radiologic diagnostic accuracy of both methods will be assessed by analyzing the number of reports that are changed after the images of the second modality become available to the radiologist in Arm 1 compared to Arm 2.

In a final approach, the diagnostic accuracy will be analyzed by retrospectively comparing all reports with the gold standard, which will be built from all available patient data at the end of the study, including all follow-up imaging studies and laboratory tests.

Secondary Outcome Measures:

- Sensitivity and specificity in ULDCT and plain film
- Frequency of change in radiological diagnosis
- Frequency of change in emergency physician's diagnosis
- Frequency of change in (planned) therapeutic course of action by emergency physician
- Frequency of accidental diagnosis in ULDCT of the chest and plain film of the chest
- Frequency of additional diagnostic imaging needed
- Frequency of unclear reports in ULDCT and plain film
- Diagnostic confidence in ULDCT and plain film by radiologist
- Diagnostic confidence in ULDCT and plain film by emergency physician

7 Inclusion criteria

Sex	All
Gender-based	No
Age limits	Minimum: 18 years Maximum: 92 years
Accept healthy volunteers	No
Participants	All patients who are assigned to a clinically indicated chest X-ray by the emergency department of Vienna General Hospital
Consent	Ability to provide informed consent Informed consent after detailed patient briefing

8 Exclusion criteria

Clinical status	A critical clinical condition that does not allow the examination with both modalities (ULDCT of the chest, chest X-ray)
Assignment	Assigned to chest X-ray as follow-up
Pregnancy	Women with positive β -HCG-test

9 Ethical considerations

- The mean effective dose of a chest X-ray examination in two views (pa, lat) is 0.08 mSv (Wachabauer and Röthlin 2017).
- The targeted mean effective radiation dose for one thoracic ultra-low-dose-CT (ULDCT) is approx. 0.2 mSv. This corresponds to approximately one month of natural background radiation in Austria. Compared to standard-dose CT examinations, ULDCT of the thorax causes about one-twentieth to one-fortieth of effective radiation dosage. Therefore, its dosage is much closer to a chest X-ray in two views than to a standard-dose CT, or even a low-dose CT examination.
- Even the cumulative dose of both examinations comes with a negligible radiation dose. Thus, no negative effects are to be expected.

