This will involve a multi-reader analysis by four radiologists in training and four specialists. All eight physicians will independently read and report all examinations by means of structured reporting. The reading time is not specified. Two groups with all 300 patients each will be created: In the 1st group, the chest X-ray examinations of Pts. 1-150 and the Ultra-Low-Dose-CT examinations of Pts. 150-300 will be available. In the 2nd group, this will be reversed. All patients will be fully anonymized and randomized. Two radiologists in training and two specialists will first read and report on group 1, the other four doctors will first read and report on group 2. Between the evaluations of group 1 and group 2 there will be at least one month to prevent a possible recognition of a case.

The gold standard will be built from all available patient data at the end of the study, including the results of all imaging procedures, follow-up examinations, physical medical examinations, laboratory and histopathological tests and further diagnostic procedures (concerns all available data, regardless of whether the patient is admitted as an inpatient).

The structured findings are then compared with the gold standard to determine the accuracy, sensitivity and specificity of both procedures.

Documentation:

- Waiting time for the ULDCT will be logged.
- Waiting time for the X-ray will be logged.

14 Statistical analysis plan

Power and sample size:

A total of 250 participants is targeted.

This is based on the following assumptions:

- Accuracy of a chest X-ray is 80%
- Accuracy of a ULDCT of the chest is 93%
- Dropout rate is 20% (one in five potential participants)

According to calculations using NQuery Advanced (version 8.3.0.0), 123 participants per arm (total of approx. 250 participants) will be required to reach a power of 85% in a one-sided test (alpha 2.5%). Due to the assumption of a dropout rate of 20% (approx. one in five potential participants), a sample size of 300 is required.

Cross tabulation and χ^2 -tests will be used to compare percentages (e.g., accuracy, sensitivity, ...). Diagnostic confidence will be compared by applying a Mann-Whitney U test.

15 Compensation

None.

Participants will not receive any compensation.

16 Study suspension

Since no negative effects on patients are expected, the trial will be suspended or stopped only if it becomes obvious that ultra-low-dose-CT examinations do not offer any benefit.

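### The gold standard, read literally, includes the ULDCT and plain film that it grades, so the gold-standard accuracy comparison is open to incorporation bias of unknown size and direction

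*Combined protocol and SAP*

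**What the plan says.** Section 13 (Retrospective) defines the reference: "The gold standard will be built from all available patient data at the end of the study, including the results of all imaging procedures". The list continues with "follow-up examinations, physical medical examinations, laboratory and histopathological tests and further diagnostic procedures", and a bracket adds that this "concerns all available data, regardless of whether the patient is admitted as an inpatient". The use of the reference follows directly: "The structured findings are then compared with the gold standard to determine the accuracy, sensitivity and specificity of both procedures".

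Section 6 gives the same rule for the final approach to the primary outcome, with a shorter list: the gold standard is "built from all available patient data at the end of the study, including all follow-up imaging studies and laboratory tests".

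On later evidence, Section 2 says "Within the trial no follow-up is intended", with the qualification that "if clinically indicated follow-ups are performed, this data may be used in the analysis phase of the study for final diagnosis". The trial's duration is given as "One year (six months of acquisition, six months of evaluation").

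Four other places matter. Section 10 gives every participant both examinations. Section 5 gives emergency physicians both reports in both arms, in different order. Section 13 (Prospective) has one radiologist write a consensus report on both methods. Section 17 promises anonymization and randomization of the evaluated data. No section says who sets the gold standard, whether that person is masked to the index tests, how the sources are weighted, or what applies when there is no other evidence.

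**The concern.** A reference that contains the test under study can count that test's errors as truth. Here the inclusive wording takes in the study ULDCT and the plain film, and no sentence takes them out again.

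How much this matters depends on how often other evidence settles the diagnosis. The plan allows plenty of such evidence but guarantees none after the visit. The cohort is recruited regardless of indication, and later data exist only where the clinicians had a reason to obtain them. Some patients may have little beyond the index images and the initial work-up, and the plan does not count them. The clinical course is not a fully independent yardstick either. It follows from decisions made with both index reports, and a consensus report, in hand.

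At stake are the gold-standard part of the primary outcome and the first-listed secondary outcome, sensitivity and specificity. The other part of the primary outcome, the number of reports changed after the second modality, does not use the gold standard and is untouched.

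**Working it through.** **1. The plan's own figure.** Section 14 assumes accuracies of 80% and 93%, one-sided alpha 2.5% and power 85%. With pooled variance and no continuity correction, n per arm = [1.96·√(2·0.865·0.135) + 1.0364·√(0.16 + 0.0651)]² / 0.13² = (0.9472 + 0.4917)² / 0.0169 = 122.5, so 123, as stated. This figure does not depend on how the reference is built. It is for two independent groups, so it does not show how many patients a restricted analysis of paired, eight-reader data would need.

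**2. Inputs for an illustration.** From Section 14: film accuracy a = 0.80 and ULDCT accuracy u = 0.93, a true gap of 13 points. Assumed, because the documents give none of them:
- a binary target;
- a share f = 25% of patients whose reference is a ULDCT reading, with a correct reference in the rest;
- r, the error correlation between two ULDCT readings, from 0 to 1;
- q, the error correlation between a film and a ULDCT reading, from 0 to 0.3.

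**3. Reference resting on ULDCT.** Within the share f:
- ULDCT agreement = u² + (1−u)² + 2r·u(1−u) = 0.8698 + 0.1302r
- Film agreement = au + (1−a)(1−u) + 2q·√[a(1−a)u(1−u)] = 0.758 + 0.2041q

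Apparent gap = 0.75·0.13 + 0.25·(0.1118 + 0.1302r − 0.2041q).

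| | r = 0 | r = 0.5 | r = 1 |
|---|---|---|---|
| q = 0 | 12.5 | 14.2 | 15.8 |
| q = 0.2 | 11.5 | 13.2 | 14.8 |
| q = 0.3 | 11.0 | 12.6 | 14.3 |

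The gap lies between about 11 and 16 points, on either side of the true 13. A larger q would lower the bottom end further.

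**4. Reference resting on film.** Take q = 0 and let s be the error correlation between two film readings. Film agreement is 0.80² + 0.20² + 2s·0.80·0.20 = 0.68 + 0.32s, and ULDCT agreement is 0.758. With f = 25% the gap is 0.0975 + 0.25·(0.078 − 0.32s), which is 11.7 points at s = 0 and 3.7 at s = 1.

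**5. Reference wrong only where both tests share the error.** Both accuracies rise by the same amount and the gap stays at 13 points.

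Inflation, attenuation and no change are therefore all possible under the same protocol wording.

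**The case against.** A composite reference from all available data is an ordinary choice in emergency diagnosis, and this one draws on laboratory, histopathological, physical and follow-up evidence for inpatients and outpatients alike. What Section 13 grades is also not the clinical report in the record but the structured findings of eight physicians. They read independently, on anonymized cases, with at least a month between the two reading groups. That stands, and it weakens the link. It does not remove it: the readers see the same images that may have set the reference, and Section 6 speaks of comparing all reports with the gold standard.

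It is also fair to say that the illustration is simpler than the endpoint. The hypothesis concerns the primary diagnosis, and Section 5 lists nine diagnoses plus a residual category. With several categories two wrong readings need not agree, so the numbers above do not carry over exactly.

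A reader might infer that the bias favours ULDCT, or that the primary outcome as a whole is invalid. The documents support neither. They do not say which index test would dominate the reference, how often, or how far errors are shared. Physicians receive both reports in both arms, so the clinical course depends on both tests and not on ULDCT alone. And the changed-reports part of the primary outcome stands outside the problem.

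**Conclusion.** The point holds as a gap in the definition of the reference. The stated rule admits the index tests to the gold standard, nothing masks whoever sets it, and in an unknown share of patients it may rest on the images it grades. This leaves accuracy against the gold standard, sensitivity and specificity open to incorporation bias.

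Neither size nor direction follows from the documents. The range of about 11 to 16 points around a true 13 rests on a binary target, the plan's assumed accuracies, an assumed 25% of references resting on a ULDCT reading, and assumed error correlations. It shows sensitivity to the reference and is not a prediction. The textual finding is firm; the magnitude is not. It should be fixed because the remedy is inexpensive, not because the comparison is shown to be wrong.

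**What to change.** Write the following into Sections 6 and 13 before any gold standard is assigned.

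1. The assessor first works from the record with the study ULDCT, the plain film and the consensus report withheld. All other evidence listed in Section 13 is used, including physical examination. The assessor records *disease established*, *absence established* (by a criterion written in advance) or *not established*.
2. Participants recorded as *not established* are flagged. Only then may the index tests complete their reference. The number flagged is reported.
3. Accuracy, sensitivity and specificity without flagged participants are prespecified as a sensitivity analysis beside the full-cohort result. Both ULDCT-minus-film differences are reported with 95% confidence intervals that allow for paired patients and multiple readers.
4. Interpretation compares the two estimates, not whether each is significant. The report states that the clinical course depends on both index tests. A change between the two results is not attributed to incorporation alone, since selection or lost precision can also produce it.

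The criterion for absence matters. Without it, patients without disease or later work-up would tend to be flagged and specificity would lose its negatives.

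The cost is protocol and SAP wording, one flag per patient and one further analysis, with no new examination or reader. Withholding the index reports at the first step adds record work for existing staff; Section 18 names one employee funded for one year. The restricted set will be less precise and may be selected, especially through loss of patients without disease, so the full-cohort result should remain the main analysis. The flag has to be set before the index results are seen, because it cannot be reliably reconstructed later.

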Martini et al. 2016; Rob et al. 2017; Moore et al. 2015) Due to the potential to reduce the radiation dose to less than 1/30 of a standard-dose CT while still providing acceptable image quality with the latest generation of devices, ULDCT of the chest is emerging as an interesting alternative to conventional chest X-ray.

To the best of the authors' knowledge, there are currently no studies comparing and evaluating ultra-low-dose-CT as a primary imaging alternative to chest X-ray in emergency department patients.

[figure not shown]
[figure not shown]
This study aims to compare ULDCT and plain film of the chest with regard to their accuracy in an unfiltered patient cohort of an emergency department. For this purpose, our ULDCT protocol will use the lowest possible dose at which image quality is diagnostically sufficient (approximately 0.2 mSv effective dose). This corresponds to less than 1/30 of the radiation dose of a standard-dose CT of the chest and to only about 2.5 times the dose of a chest X-ray in two views. This dose is equal to less than a month of natural background radiation in Austria and less than the radiation exposure on an intercontinental flight. (Bundesministerium für Arbeit, Soziales, Gesundheit und Konsumentenschutz 2018b; Bundesministerium für Arbeit, Soziales, Gesundheit und Konsumentenschutz 2018a; Ditto et al. 2013)

[figure not shown]
In addition to the accuracy of ULDCT of the chest compared to plain film of the chest, this trial also aims to analyze the clinical relevance of both methods by assessing the respective impact on final diagnosis, as well as possible changes in therapy.

5 Study Design

Study Type	Interventional
Primary Purpose	Diagnostic
Number of Arms	2
Masking (prospective)	None (open label)
Allocation	Randomized
Enrolment	250

Arms	Assigned Interventions

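### The enrolment target is 250 in Sections 2, 5 and the opening of 14 but 300 later in 14 and in 13, and the 250 contains no allowance for the stated 20% dropout

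*Combined protocol and SAP*

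**What the plan says.** Three places give 250:

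- Section 2: "Intended number of participants 250".
- Section 5: "Enrolment 250".
- Section 14, opening line: "A total of 250 participants is targeted".

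Two places give 300:

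- Section 14, after the power calculation: "Due to the assumption of a dropout rate of 20% (approx. one in five potential participants), a sample size of 300 is required".
- Section 13, retrospective reading: "Two groups with all 300 patients each will be created". In the first group, "the chest X-ray examinations of Pts. 1-150 and the Ultra-Low-Dose-CT examinations of Pts. 150-300 will be available"; the second group reverses this.

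Section 14 says the 250 rests on three assumptions: X-ray accuracy 80%, ULDCT accuracy 93%, and "Dropout rate is 20% (one in five potential participants"). It then reports that "123 participants per arm (total of approx. 250 participants) will be required to reach a power of 85"%, one-sided at 2.5%.

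Two other passages bear on the reading. Under Section 10, only patients who are eligible and consent become participants and have the ULDCT. Section 2 puts participation at about two hours, with no trial follow-up.

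**The concern.** A reader cannot tell whether recruitment should stop at 250 or at 300, and either could later be described as planned. The number also decides how many people have a study ULDCT on top of their indicated X-ray.

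The plan does not label 250 as evaluable and 300 as enrolled, and Section 5 attaches the word enrolment to 250. If dropout really is one of the bases of 250, then 250 should already contain the allowance and 300 would be unnecessary. If it is not, then 250 enrolled leaves almost no margin for loss. At stake are the enrolment target itself, the 85% power claim, and the case set for the multi-reader analysis.

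**Working it through.** **Inputs (Section 14).** p1 = 0.80, p2 = 0.93, difference 0.13, mean 0.865; one-sided alpha 0.025 (z = 1.960); power 85% (z = 1.036); dropout 20%. Allocation is half and half (Section 5).

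**Reproducing the plan's figure.** Two independent proportions, pooled variance under the null, no continuity correction:

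n per arm = [1.960 × √(2 × 0.865 × 0.135) + 1.036 × √(0.80 × 0.20 + 0.93 × 0.07)]² / 0.13² = 122.5, rounded up to 123.

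This matches the plan. 2 × 123 = 246, and 250 leaves 4 spare (1.6%). Dropout does not enter the formula.

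**Dropout inflation.** 246 / 0.8 = 307.5, so 308; 250 / 0.8 = 312.5, so 313. The plan's 300 equals 250 × 1.2. Conversely, 300 × 0.8 = 240 and 250 × 0.8 = 200.

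**Power by the same formula**, with exact enumeration of the pooled z-test where run:

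| Enrolled | Lost after enrolment | Evaluable per arm | Power (formula) | Power (exact) |
|---|---|---|---|---|
| 300 | 0% | 150 | 91.3% | 92.3% |
| 300 | 20% | 120 | 84.3% | 85.7% |
| 250 | 0% | 125 | 85.7% | 86.8% |
| 250 | 5% | 118.75 | 83.9% | – |
| 250 | 10% | 112.5 | 81.9% | – |
| 250 | 20% | 100 | 77.1% | 79.0% |

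With 250 enrolled, 85% power tolerates a loss of 1 − 122.5/125 = 2.0%. For 80% power the requirement is 107.3 per arm, so the tolerated loss is 1 − 107.3/125 = 14.2%.

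**Can one reading fit every passage?**

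| Reading | What it contradicts |
|---|---|
| 300 enrolled, 20% lost afterwards | 250 in Sections 2 and 5; about 240 remain, so not all 300 for Section 13 |
| About 300 approached, 20% lost before enrolment, 250 enrolled | 300 × 0.8 is 240, not 250; Section 13 needs both examinations in 300 patients, but only participants have the ULDCT |
| 250 enrolled, 20% lost afterwards | Section 14's statement that dropout requires 300; Section 13's 300 |

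Each reading needs at least one passage changed.

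**Reading load in Section 13.** 300 patients × 2 examinations × 8 readers = 4,800 reads. An enrolment of 250 allows at most 250 × 2 × 8 = 4,000.

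**Scope of the power figures.** They apply to 80% versus 93% in two separate arms. For both modalities in the same 200 patients, one read each, the McNemar normal approximation with difference 0.13 gives 94.8% power at the largest possible discordance (0.20 + 0.07 = 0.27). It gives 96.7% with independent errors (discordance 0.80 × 0.07 + 0.20 × 0.93 = 0.242), and over 99.9% at the smallest (0.13).

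**The case against.** Section 14 can be read as an ordinary two-step derivation: about 250 evaluable, then 300 after a dropout allowance, with 250 × 1.2 giving exactly 300. On that reading 250 ought to contain no allowance, and listing dropout among its assumptions is only loose drafting. Alternatively, dropout is described in terms of potential participants, and a two-hour participation without follow-up leaves little room for later loss. Then 250 enrolled is close to coherent, and Section 13 is the main passage that fails. Either way power is about 84% to 86%. The 77% case requires setting aside the sentence that asks for 300. Even then, the within-patient comparison against the gold standard stays well powered, and the between-arm measure in Section 6 counts changed reports, not accuracy.

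Much of this stands. The 77% is a conditional worst case, and no shortfall has been shown for the paired accuracy comparison. The gap between 300 and 308 or 313 is minor. But the two charitable readings give different enrolment numbers, and the plan does not choose between them. The first contradicts the enrolment entry in Section 5; the second cannot supply the 300 patients in Section 13. The objection limits the consequence but does not remove the contradiction.

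**Conclusion.** The concern holds. The current text gives two enrolment targets 50 participants apart, and the stated basis for 250 is wrong on the plan's own figures, because 123 per arm contains no dropout term.

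Whether 85% power is kept depends on the reading: roughly yes for 300 enrolled with 20% lost or 250 enrolled with no later loss, and no for 250 enrolled with 20% lost afterwards. These figures assume Section 14's accuracies, equal arms and an uncorrected chi-square test. The case for correction rests on the contradictory target, not on a demonstrated loss of power. It must be fixed, because the target governs when recruitment stops and how many people have a study ULDCT.

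**What to change.** State one enrolment figure in Sections 2, 5, 13 and 14. Label 123 per arm (246, about 250) as the evaluable requirement. Move the 20% dropout from the assumptions behind 250 to the enrolment figure, and say whether it is counted before or after enrolment. Then use whichever statement matches the authors' intent:

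- (a) 300 enrolled, about 240 evaluable after 20% dropout, power about 84%; 308 enrolled if 85% is to be kept strictly by the formula.
- (b) About 310 approached, 20% lost before enrolment, 250 enrolled with no material loss afterwards, power about 85%; Section 13 changed to 250.
- (c) 250 enrolled, about 200 evaluable after 20% loss, power about 77% for the two-arm comparison; Section 13 changed to match.

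In Section 13, replace the fixed 300 and the two patient ranges, which both include patient 150, with all patients who have both examinations, split into two non-overlapping halves.

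The cost is wording only under (b) and (c), and under (a) if 300 was already intended. Option (c) means reporting a less favourable power. If recruitment was really set at 250, choosing (a) adds 50 participants, each with a study ULDCT in addition to the indicated X-ray.

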- A delay in diagnosis can be ruled out since each examination is promptly evaluated – before the examination for the second imaging modality is performed.
- Since no contrast medium is applied, adverse effects or events – in this context – can be ruled out.

10 Recruitment

All patients who are assigned to receive a clinically indicated chest X-ray by the emergency department of Vienna General Hospital – regardless of indication – are offered participation in this trial. Thus, only clinically indicated cases may be included.

Patients who meet the eligibility criteria and provide informed consent become participants in this trial and receive an ultra-low-dose-CT examination of the thorax in addition to a chest X-ray.

11 Study duration

Based on a preliminary analysis of frequency, the anticipated total study duration, including analysis of all parameters, is one year.

12 Radiation dose

- Chest X-ray: The reference dose for a chest X-ray in two views is approx. 0.08 mSv (effective dosage) (Wachabauer and Röthlin 2017).
- Thorax-ULDCT: based on recent publications regarding imaging in emphysema and dyspnea, as well as on measurements with a thorax-CT test-phantom performed with the specific CT devices used for the study (Siemens Somatom Drive and Siemens Somatom Force), an effective dose of approx. 0.2 mSv (corresponding to DLP 12.5) appears to be optimal for ULDCT (lowest dose possible with sufficient image quality). This dose is below the effective dose of one month of natural background radiation, which is referenced as 0.23 mSv per month in Austria (2.8 mSv per year). (Bundesministerium für Arbeit, Soziales, Gesundheit und Konsumentenschutz 2018a; Bundesministerium für Arbeit, Soziales, Gesundheit und Konsumentenschutz 2018b; Ditto et al. 2013)

The thorax-CT test-phantom used is model RS-111 by "Radiology Support Devices", Long Beach, California, USA.

13 Radiological analysis

Rationale behind the study design:

Prospective:

For ethical, practical, and legal reasons, the emergency physician always needs an immediate consensus report on both methods written by a single specialist in radiology in order to make a final treatment decision. This would not be possible without a significant delay, if two radiologists had to create two separate reports. The frequency with which diagnoses and therapies by radiologists and emergency physicians differ between Arm 1 and Arm 2 will be measured.

Retrospective:

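### The eight-reader comparison of ULDCT with plain film is paired and clustered, but Section 14 names only cross tabulation and chi-square tests and gives no rule for combining readers

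*Combined protocol and SAP*

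**What the plan says.** Under Section 10, participants "receive an ultra-low-dose-CT examination of the thorax in addition to a chest X-ray", so each patient contributes to both modalities.

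Section 13 (Retrospective) states: "This will involve a multi-reader analysis by four radiologists in training and four specialists". It continues: "All eight physicians will independently read and report all examinations by means of structured reporting". The material is split into two reading sets: "Two groups with all 300 patients each will be created", with the modalities swapped between the sets. Each reader therefore sees both examinations of every patient. The purpose is explicit: "The structured findings are then compared with the gold standard to determine the accuracy, sensitivity and specificity of both procedures".

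Section 6, under the primary outcome, adds: "In a final approach, the diagnostic accuracy will be analyzed by retrospectively comparing all reports with the gold standard".

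For the prospective part, Section 13 mentions only change frequencies: "The frequency with which diagnoses and therapies by radiologists and emergency physicians differ between Arm 1 and Arm 2 will be measured".

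Section 14 names cross tabulation and chi-square for all of this ("tests will be used to compare percentages (e.g., accuracy, sensitivity" and so on) and Mann-Whitney U for diagnostic confidence. It names no McNemar test, mixed or marginal model, cluster-robust variance or multi-reader method. Averaging, pooling, majority vote and per-reader reporting are not mentioned. The only consensus report in the document is the clinical one in the prospective part.

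**The concern.** An ordinary chi-square test assumes independent observations. The reader study breaks that assumption twice: the two modalities are observed in the same patients, and each image is read eight times. Positive correlation between modalities makes the true variance of the difference smaller than the test assumes. Agreement among readers on the same image makes it larger. The net effect can go either way.

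The missing combination rule is a second problem. Eight separate tests, subsets of trainees or specialists, or one pooled table could each claim to follow the plan, and they could disagree. The choice would be made after the data are seen.

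This reading is the natural meaning of the gold-standard comparison in the primary outcome, because Section 13 assigns accuracy, sensitivity and specificity to it.

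**Working it through.** **1. The plan's own figure.** Inputs from Section 14: accuracy 80% and 93%, one-sided alpha 2.5%, power 85%. For two independent groups with pooled variance, the mean accuracy is 0.865 and

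n = [1.960·√(2·0.865·0.135) + 1.036·√(0.80·0.20 + 0.93·0.07)]² / 0.13² = 122.5, that is, 123 per arm.

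This reproduces the stated figure. A McNemar calculation for the same difference needs 125.4, 98.3 or 71.2 pairs in total at a between-modality correlation of 0, 0.25 or 0.5 (assumed). So 123 per arm is a two-group figure. With Mann-Whitney U named for confidence, this suggests that an unpaired chi-square is meant. That is an inference, and steps 3 and 4 cover both readings.

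**2. One reader, pairing ignored.** With r1 the correlation between modalities for the same reader, the true variance is (1 − r1) times what chi-square assumes. The one-sided error is 1 − Φ(1.96/√(1 − r1)):

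- r1 = 0.25: 1.2%
- r1 = 0.50: 0.3%

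The nominal value is 2.5%, so the test is conservative.

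**3. Eight readers pooled as independent.** Let r2 be the correlation between different readers on the same modality, and r3 that between different readers on different modalities. Per patient, the reader-averaged difference has variance 2pq(1 − r1 + 7r2 − 7r3)/8, while chi-square assumes 2pq/8. Hence

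R = 1 − r1 + 7(r2 − r3), and the two-sided error is 2[1 − Φ(1.96/√R)], whatever the number of patients.

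McNemar pooled over readers assumes 2pq(1 − r1)/8, so its ratio is R/(1 − r1).

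Example: r2 = 0.5, r1 = r3 = 0.25 gives R = 0.75 + 7·0.25 = 2.5. The chi-square error is 21.5% two-sided, or 10.8% one-sided. For McNemar the ratio is 2.5/0.75 = 3.33 and the error 28.3%.

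Two-sided error at nominal 5%, for r2 from 0.2 to 0.5 (all correlations assumed):

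| r3/r2 | Chi-square, r1 = r3 | Chi-square, r1 = r3 + 0.2 | McNemar, r1 = r3 | McNemar, r1 = r3 + 0.2 |
|---|---|---|---|---|
| 1/2 | 12–22% | 10–20% | 14–28% | 17–34% |
| 3/4 | 7–11% | 5.0–8.6% | 10–21% | 11–26% |
| 7/8 | 5% | 2.8% | 7.5–14% | 8–19% |
| 1 | 0.6–2.8% | 0.03–1.1% | 5% | 5% |

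On the plan's one-sided 2.5% scale, halve each entry.

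**4. Simulation.** Settings: 300 patients, 8 fixed readers, 2 modalities, equal accuracy 86.5%, probit model, 2,500 runs. Two-sided rejection rates at nominal 5%:

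| r1 / r2 / r3 | Pooled chi-square | Pooled McNemar | Paired test of reader-averaged difference |
|---|---|---|---|
| 0.09 / 0.21 / 0.09 | 13.0% | 15.6% | 4.9% |
| 0.31 / 0.20 / 0.20 | 1.8% | 5.3% | 5.1% |
| 0.31 / 0.43 / 0.21 | 20.6% | 29.0% | 4.4% |
| 0.59 / 0.43 / 0.43 | 0.2% | 5.6% | 5.4% |

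The patient-level paired test stays close to 5%; the pooled chi-square does not, and pooled McNemar does so only where r2 = r3.

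**5. Power for one reader, one-sided 2.5%, correlation 0.25 to 0.5.** At the planned 80% versus 93% with 240 pairs (300 × 0.8), the unpaired test has 99.5–99.9%. At an assumed 87% versus 93% with 300 pairs, it has 71–75% and McNemar 80–92%.

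**6. Readers as a sample.** If conclusions are to extend beyond these eight readers, reader-by-modality variation with SD τ adds τ²n/(pq) to R. With τ = 0.01 and n = 300 this is 0.0001·300/(0.865·0.135) = 0.257. The pooled chi-square errors for r1 = r3 then run from 2.4% to 24%.

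**The case against.** The strongest reply is that the plan prescribes no pooling, so the large error rates belong to an analysis it never states. They also rest on assumed correlations, and some cells sit at exactly 5%. That is fair as a description of the figures: they show how far the result depends on the missing rule, not a demonstrated error. It does not rescue the plan, because the one named test is miscalibrated for these data under most assumptions, and the single-reader alternative gives eight answers without a decision rule.

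Secondly, the powered contrast may be untouched. The reports to be compared with the gold standard could include the first prospective reports, plain film in one arm and ULDCT in the other. Those are different patients, and chi-square suits them. This stands as a possible reading. On it, the defect is confined to the reader study, where sensitivity and specificity, both listed secondary outcomes, are still affected.

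Thirdly, chi-square might loosely include McNemar. Pooled over eight readers, McNemar also ignores clustering and has the right level only when r2 = r3.

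Finally, Section 17 requires complete anonymization, while pairing needs a code that links a patient's two examinations. Comparison with the gold standard already requires such a link.

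**Conclusion.** The concern holds, and the plan should be changed before analysis. For the reader study, Section 14 names a test that does not fit the data structure and gives no rule for reaching one conclusion from eight readers. The omission is certain; the size and direction of the effect are not, because the documents give no correlations. Under the assumed ranges, the pooled chi-square error is 0.03% to 22% against 5% two-sided. The single-reader test that ignores pairing loses power at smaller differences.

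The planned 13-point difference is large enough that the overall accuracy conclusion would probably survive. The exposure lies in a smaller true difference and in sensitivity and specificity, which rest on subsets of patients. Power for the multi-reader analysis, or for sensitivity and specificity, cannot be computed from the documents.

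**What to change.** In Section 14:

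1. For the retrospective comparison of accuracy, sensitivity and specificity, replace chi-square with one prespecified analysis of the reader-averaged within-patient difference that respects pairing and clustering by patient and reader, for example a multi-reader multi-case analysis. State whether the eight readers are fixed or a sample of readers. Report single-reader McNemar results as descriptive only.
2. Keep chi-square and Mann-Whitney U for contrasts between the randomized arms, where the patients differ.
3. State which reports the gold-standard comparison in Section 6 covers, and that 123 per arm with 85% power refers to two independent groups.

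The cost is SAP wording and slightly more analysis work. Intervals will be wider if readers are treated as a sample. Data collection does not change, provided the anonymized data keep a study code linking each patient's two examinations.
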